4.4. Post-Viremia Follow-Up

Following resolution of viremia, subjects will return to the previous sampling schedule (approximately every 4 weeks, \pm 14 days) for an additional 6 months (or until another study termination endpoint is reached, whichever occurs sooner). The first follow-up visit should occur approximately 4 weeks after the BK viral load was documented to be negative.

Subjects will remain in the post-viremia follow-up phase: 1). for 6 months following resolution of the BK viremia; 2). until another study termination endpoint is reached; 3). until death; 4). until they decided to terminate participation; 5). until the investigator decides that the subject should terminate participation; or 6). until the study closes (whichever occurs first). Reason for termination of study participation will be documented.

4.5. Specimens for Biomarker Studies

Detection of tubular injury by measurement of biomarkers may provide an opportunity to manage renal graft recipients at an earlier stage before invasive BK disease. Coupled with urine PCR, detection of renal tubular injury in recipient urine is a simple technique. Urine markers of injury have already been identified in other causes of acute kidney injury and are commercially available. These include cystatin C, renin, clusterin, Kim-1, b2-microglobulin, osteopontin, retinol binding protein, and markers of cell apoptosis. For biomarker studies, approximately 100 mL of urine will be collected, aliquoted and stored at -70°C on each subjects at each scheduled study visit (see MOP for details). Urine will also be collected at the time of any renal biopsy, if performed. We will retrospectively analyze expression of these urine markers of injury using urine specimens collected at the time of detection of BK virus (in urine and/or blood) and at serial time-points. Using appropriate control specimens, values will be compared for: 1) Subjects who are BK viremic vs. non-viremic; 2) Subjects who subsequently develop BKVN vs. subjects with stable GFR vs. subjects with declining GFR attributed to a cause other than BKVN.

4.6. Documenting Special Events

Specific clinical events and outcomes that may be related to BKV infection will be recorded, including:

- subject death
- loss of graft function as defined by $\text{GFR} < 10 \text{ mL/min/1.73 m}^2$
- development of urinary outlet obstruction
- development of gross hematuria

- development of lymphocele
- acute rejection
- initiation of dialysis
- re-transplantation
- renal biopsies – Should renal biopsy be performed per standard-of-care during the course of the study, results will be submitted using information from the pathology report.

All data will be recorded on source documents, then entered on eCRFs and submitted electronically.

4.7. Adverse Events

No protocol-defined interventions are included in this study; thus, adverse event recording will not be required unless the event is related to a study-mandated procedure (e.g., phlebotomy).

4.8. Clinical Laboratory Data

Specimens for laboratory studies will be collected as detailed in Section 7.2.

4.9. Study Visits

The study visits for the screening phase will be every 4 weeks \pm 7 days for 6 months (timed from date of transplantation) and then every 8 weeks \pm 14 days. The study visits during the intensive monitoring period are every 2 weeks \pm 7 days until resolution of BK viremia and then every 4 weeks \pm 7 days for 6 months.

Because the first year following kidney transplantation is challenging for patients, all post-enrollment study visits and visit windows are approximations and may fluctuate with study subject availability.

Events occurring at each study visit are listed in Appendix A.

5. STUDY POPULATION

5.1. Study Population Selection

All adult renal or renal-pancreas transplant patients who meet protocol inclusion/exclusion criteria are eligible for participation in this study.

In an effort to capture subjects early in the course of the evolving BK infection and avoid subjects who have already developed evidence of BKVN, this protocol will emphasize consent in the early peri-transplant period. Patients may be consented while hospitalized pre-transplantation (as early as 7 days prior to transplantation) or at an outpatient follow-up visit (as late as 100 days post-transplantation). The study enrollment visit and initial collection of protocol-defined specimens will take place between 4 weeks and 100 days following renal or renal/pancreas transplantation.

5.2. Inclusion of Women, Children and Minorities

All adult renal or renal/pancreas transplant patients meeting protocol inclusion/exclusion criteria will be potentially eligible for participation in this study. Subjects will not be excluded on the basis of gender or ethnicity. Since there is no known gender or ethnic predilection for BKV infection, it is expected that the percentage of women and minorities included in the study will reflect the local demographics of the renal or renal-pancreas transplant population at the participating sites.

5.3. Inclusion/Exclusion Criteria

5.3.1. Inclusion Criteria

- Renal or renal-pancreas transplant patients who are within the informed consent window (as early as 7 days prior to transplantation or as late as 100 days post-transplantation).
- Age \geq 18 years;
- Willing and able to understand and provide written informed consent.

5.3.2. Exclusion Criteria

- Evidence of proven or suspected BKVN by clinical or pathologic diagnostic criteria;
- Initiation of chronic dialysis post-transplantation due to graft failure.

6.0. SCHEDULE OF EVENTS

6.1. Enrollment Visit (Day 1)

Subjects who meet criteria for the eligibility criteria and have provided informed consent should be scheduled for an Enrollment Visit. The enrollment visit should be scheduled no sooner than 4 weeks after the transplant, but not more than 100 days after the transplant. At the initial Enrollment Visit, the following assessments should be performed:

1. Confirm that informed consent has been obtained and that the subject still wishes to participate;
2. Review the inclusion-exclusion criteria to assure that the patient remains eligible for study participation. Subjects who are not willing or eligible to participate in the clinical trial should be logged as screen failures and reported on the Failed Screening page located on the Central Unit website.
3. Record donor and recipient demographic and risk factor data, to include:
 - a. Donor-derived factors:
 - i. Deceased donor – Standard criteria donor (SCD), Donor after cardiac death (DCD), Expanded criteria donor (ECD)
 - ii. Living donor – related donor or unrelated donor
 - iii. ABO incompatibility
 - iv. Total HLA mismatches
 - v. HLA C7 status
 - vi. Age
 - vii. Race/ethnicity
 - viii. Sex
 - b. Recipient-derived factors:
 - i. Delayed graft function (DGF), defined as use of dialysis within 7 days of the transplant
 - ii. Cold ischemia time (CIT)
 - iii. Warm ischemia time (WIT)
 - iv. Use of stents
 - v. HLA C7 status
 - vi. Type/intensity of immunosuppression, including corticosteroids
 - vii. Acute rejection
 - viii. Age
 - ix. Race/ethnicity
 - x. Sex
4. Document medical and surgical history
5. Document use of selected concomitant medications (specifically, antiviral agents, immunomodulators, and immunosuppressive medications – see the listing provided in

- the MOP). Record all immunosuppressive drugs administered since transplantation, including peri-operative induction therapy with biological agents;
6. Document blood concentrations of immunosuppressive drugs measured for clinical reasons;
 7. Obtain blood for serum creatinine determination and estimated GFR (if these studies were performed for routine standard-of-care within 7 days prior to enrollment, then the results of those assays can be recorded for study purposes);
 8. Collect 10 ml of blood for study-specified PCR assays (BK and other viruses), to be performed at the UAB Central Laboratory. Blood will be collected, separated to plasma, then stored and shipped per instructions in the Manual of Procedures;
 9. If blood BK PCR was performed for routine standard-of-care in a local or reference laboratory, record the results of that assay as well. (Specimen for PCR will still be submitted to the UAB Central Laboratory);
 10. Optional urinalysis - if UA was performed for routine standard-of-care with 7 days of enrollment, then the results of those assays can be recorded;
 11. Obtain a urine sample (approximately 100 ml) for study-specified PCR assays (BK and other viruses) and measurements of urinary biomarkers to be performed at the UAB Central Laboratory. Urine will be collected, stored, and shipped per instructions in the Manual of Procedures.
 12. Notify the UAB Central Unit if the subject has consented to any other research study.

6.2. Screening Study Visits (approximately every 4 weeks +/- 7 days for 6 months and then approximately every 8 weeks +/- 14 days for 6 months)

At each subsequent protocol-defined screening visit, the following events will occur:

1. Document interval medical history to specifically include:
 - a. subject death,
 - b. loss of graft function as defined by $GFR < 10 \text{ mL/min/1.73 m}^2$
 - c. development of urinary outlet obstruction
 - d. development of gross hematuria
 - e. development of lymphocele
 - f. acute rejection
 - g. initiation of dialysis
 - h. re-transplantation
 - i. renal biopsies – Should renal biopsy be performed per standard-of-care during the course of the study, record the results from the pathology report.
2. Document use of selected concomitant medications (specifically, antiviral agents, immunomodulators, and immunosuppressive medications – see MOP for listing);
3. Record blood concentrations of immunosuppressive drugs obtained for clinical care purposes;

4. Obtain blood for serum creatinine determination and estimated GFR (if these studies were performed for routine standard-of-care within 7 days prior to the study visit, then the results of those assays can be recorded for study purposes);
5. Obtain 10 ml of blood for study-specified PCR assays (BK and other viruses), to be performed at the UAB Central Laboratory. Blood will be collected, separated to plasma, then stored and shipped per instructions in the Manual of Procedures; If blood BK PCR was performed for routine standard-of-care at a local or reference laboratory, record the results of that assay in the research record;
6. Optional urinalysis - if UA was performed for routine standard-of-care within 7 days of enrollment, then the results of those assays can be recorded);
7. Obtain urine (approximately 100 ml) for subsequent study-specified PCR assays (BK and other viruses) and measurements of urinary biomarkers to be performed at the UAB Central Laboratory. Urine will be collected, stored, and shipped per instructions in the Manual of Procedures.
8. Notify the UAB Central Unit if the subject has consented to any other research study.

6.3. Intensive Monitoring Phase for BK Viremic Subjects: (approximately every 2 weeks +/- 7 days until viremia has resolved (PCR negative or <1000 copies/ml), then approximately every 4 weeks +/-14 days for 6 months).

At each protocol-defined study visit, the following events will occur:

1. Document interval medical history to specifically include:
 - a. subject death,
 - b. loss of graft function as defined by GFR <10 mL/min/1.73 m²
 - c. development of urinary outlet obstruction
 - d. development of gross hematuria
 - e. development of lymphocele
 - f. acute rejection
 - g. initiation of dialysis
 - h. re-transplantation
 - i. renal biopsies – Should renal biopsy be performed per standard-of-care during the course of the study, record the results from the pathology report.
2. Document use of selected concomitant medications (specifically, antiviral agents, immunomodulators, and immunosuppressive medications – see MOP for listing);
3. Record blood concentrations of immunosuppressive drugs obtained for clinical care purposes;
4. Obtain blood for determination of creatinine and GFR. If results of serum creatinine and GFR obtained for clinical care purposes (within 7 days) are available, those results may be used instead;

5. Obtain 10 ml of blood for study-specified PCR assays (BK and other viruses), to be performed at the UAB Central Laboratory. Blood will be collected, separated to plasma, then stored and shipped per instructions in the Manual of Procedures;
6. If blood BK PCR was performed for routine standard-of-care at a local or reference laboratory, record the results of that assay in the research record;
7. Optional urinalysis – if results of urinalysis obtained for clinical care purposes (within 7 days) are available, those results may be recorded;
8. Obtain urine (approximately 100 ml) for subsequent study-specified PCR assays (BK and other viruses) and measurements of urinary biomarkers to be performed at the UAB Central Laboratory. Urine will be collected, stored, and shipped per instructions in the Manual of Procedures.
9. Notify the UAB Central Unit if the subject has consented to any other research study.

6.4. Subject Early Termination

Subjects will be terminated from the study for any of the following reasons:

- Death;
- Initiation of chronic dialysis for loss of graft function;
- Re-transplantation;
- Inability or unwillingness to comply with study requirements.

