BK polyomavirus infection is mediated by direct infection of allograft renal tubular epithelial cells (TECs). Molecular analysis has demonstrated that there is substantial inflammatory injury associated with a profibrotic milieu.¹⁶ Monitoring for infection is performed by detecting viral copies in urine and blood. However, virus is frequently shed in the urine in the absence of invasion leaving the urinary monitoring as a suboptimal screening mechanism in terms of management of recipients that are infected. A testable hypothesis is that tubular injury, in the context of viral infection, indicates invasive disease. Detection of this tubular injury may provide an opportunity to manage kidney graft recipients at an earlier stage before invasive BK disease. Coupled with urine PCR, detection of renal tubular injury in recipient urine is a simple technique. Urine markers of injury have already been identified in other causes of acute kidney injury and are commercially available. These include cystatin C, renin, clusterin, Kim-1, b2-microglobulin, osteopontin, retinol binding protein, and markers of cell apoptosis.

Currently, no antiviral drug is approved for treatment of BKV infection.¹⁷ Anecdotal reports have claimed benefit from cidofovir, leflunomide, quinolone antibiotics, and intravenous immunoglobulin. However, the current standard of care is early screening for BKV viremia and reduction in immunosuppressive therapy in an effort to improve graft survival, although it has not been studied in a controlled fashion.^{12,18,19} At some institutions, modulation of immunosuppressive therapy has dramatically reduced the rate of allograft loss due to BKVN.¹⁴ Reduction in the immunosuppressive regimen is not without consequence and can result in graft loss from immune-mediated organ rejection.²⁰ Despite reduction in immunosuppression, in some studies 30 to 70% of patients with BKVN have progressive deterioration in renal function, eventually resulting in allograft loss. Declining renal function typically occurs over months and is thought to result from a combination of persistent viral infection, organ rejection (induced by reduction in immunosuppression), and renal fibrosis.

This study is being performed to identify the natural history of BK viremia in renal transplant patients with the intent to identify high-risk groups that may benefit in the future from therapy with

safer and more effective antiviral medications.

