3.2.2. Secondary endpoints

- Timing of onset of BK viremia (number of days post-transplant)

- Duration of BK viremia
- Incidence of BKVN in the study population
- Dynamics of quantitative measurements of BK viremia over time
- Frequency of donor and recipient-related risk factors for BV viremia, including:
 - a. Donor-derived factors:
 - i. Deceased donor – Standard criteria donor (SCD), Donor after cardiac death (DCD), Expanded criteria donor (ECD)
 - ii. Living donor – related donor or unrelated donor
 - iii. ABO incompatibility
 - iv. Total HLA mismatches
 - v. HLA C7 status
 - vi. Race/ethnicity
 - vii. Sex
 - b. Recipient-derived factors:
 - i. Delayed graft function (DGF), defined as use of dialysis within 7 days of the transplant
 - ii. Cold ischemia time (CIT)
 - iii. Warm ischemia time (WIT)
 - iv. Use of stents
 - v. HLA C7 status
 - vi. Type/intensity of immunosuppression, including corticosteroids
 - vii. Acute rejection
 - viii. Age
 - ix. Race/ethnicity
 - x. Sex
- Frequency of clinical outcomes that are potentially related to BKV infection, including:
 - a. subject death,
 - b. loss of graft function as defined by GFR <10 mL/min/1.73 m²
 - c. development of urinary outlet obstruction
 - d. development of gross hematuria
 - e. development of lymphocele
 - f. acute rejection
 - g. initiation of dialysis
 - h. re-transplantation
 - i. renal biopsies

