We are also interested in comparing the change in GFR between those with and without BKV viremia. In this power analysis, we will only be concerned about the change from baseline (time of enrollment) to Month 12 (time post-transplant). Assuming the standard deviation of the change in GFR is assumed to be the same for those with and without BKV viremia and equals 10.9 ml/min/1.73 m² (Ref: Srinivas TR, Flechner SM, Poggio ED, et al. Glomerular filtration rate slopes have significantly improved among renal transplants in the United States. Transplantation 2010; 90:1499-505.). With 40 BKV viremia subjects and 410 non-BKV viremia subjects, we will detect a mean difference in the change in GFR of at least 5.9 ml/min/1.73 m² with 90% power between these two groups of subjects at 5% level of significance based on a t-test. In the final analysis, we will be using all available GFR data for each subject which should increase the power as more information is used. This will enable us to still use data from subjects who dropped out before the end of the study.

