8.4. Final Analysis Plan

All statistical tests will be performed at 5% significance level and confidence interval at 95% level. There will be no adjustment on the levels for multiple testing. There will also be no imputation methods that will be used for missing data. Any viral load <100 (i.e., undetectable) will be replaced by viral load value of 10. Quantitative viral loads will be analyzed based on the log based 10 transformation.

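### The GFR comparison has no rule for graft loss: values after dialysis or re-transplantation are absent, which biases the viremic deficit toward zero if viremic subjects lose grafts more often

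*Combined protocol and SAP*

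**What the plan says.** - **Leaving the study.** Section 6.4 lists "Initiation of chronic dialysis for loss of graft function" as a reason for termination, along with re-transplantation and death. Section 4.2 also names graft failure for subjects still in screening. A GFR below 10 is not by itself a termination reason in section 6.4.
- **Missing data.** Section 8.4: "There will also be no imputation methods that will be used for missing data".
- **GFR analysis.** Section 8.4.1 compares GFR over time by viremia status with a mixed model for repeated measures on every recorded value. Section 8.2.1 presents this as the way in which data from dropouts are still used. Nowhere is a value, rank or composite given for GFR after graft loss or death, and no sensitivity analysis for informative dropout is planned.
- **Standing of the comparison.** It is a primary objective (section 3.1.1), the stated hypothesis (section 8.1) and part of the primary outcome analysis (section 8.4.1). The only primary endpoint listed in section 3.2.1 is incidence of viremia.
- **Recorded events.** Section 3.2.2 counts "loss of graft function as defined by GFR <10" mL/min/1.73 m², dialysis, re-transplantation and death as secondary outcomes. Sections 6.2 and 6.3 document them at visits.
- **Background.** Section 2.1.1 says that virtually all patients who progress to BKVN are viremic. It adds that in some studies, despite reduced immunosuppression, "30 to 70% of patients with BKVN have progressive deterioration in renal function" and eventually lose the graft.

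**The concern.** The absence of imputation is not in itself the fault. A likelihood-based mixed model needs none, provided that the chance of a value being missing depends only on values already recorded. That condition is doubtful here, because participation ends when the outcome itself has collapsed. After that point the model fills in, implicitly, the course of subjects who are still under observation and had similar earlier values. It therefore estimates the mean GFR change as if the lost grafts had continued.

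The protocol's reasoning runs from viremia to BKVN to graft loss, and section 8.1 expects viremia to lower GFR. A higher loss rate among viremic subjects is thus what the protocol itself leads one to expect, and the omission would then pull the estimated deficit toward zero, against the study's hypothesis. The viremic group is small: with 40 subjects, one graft loss is 1/40 = 2.5% of the group. Counting graft loss separately as a secondary outcome does not correct the GFR estimate.

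**Working it through.** **1. The plan's own figure.** For 40 viremic and 410 non-viremic subjects and an SD of change of 10.9, section 8.2.1 states: "we will detect a mean difference in the change in GFR of at least 5.9 ml/min/1.73 m²". Power is put at 90%, for a t-test at the 5% level. Sidedness is not given; two-sided is assumed.

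- SE = 10.9 × √(1/40 + 1/410) = 10.9 × 0.1657 = 1.806
- Power = Φ(5.9/1.806 − 1.96) = Φ(1.31) ≈ 0.90 (0.9045 unrounded; 0.9033 with the noncentral t on 448 df)
- Difference detectable with 90% power: 5.87

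The figure reproduces (one-sided 5% would give 0.947). It contains no allowance for graft loss.

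**2. Simulation of the planned model.** The documents give no graft-loss rate by group, baseline GFR or pattern of decline, so these inputs are assumptions:

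- 40 viremic and 410 non-viremic subjects; GFR at Months 1 to 6, 8, 10 and 12
- baseline GFR mean 55, SD 12; individual slopes with SD 10 over 11 months; residual SD 4. The implied SD of change is √(10² + 2 × 4²) = 11.5, close to the plan's 10.9
- viremic deficit of 3 over 11 months apart from graft loss
- first missing visit after graft loss drawn at random from Months 5, 6, 8, 10 and 12; true value set to 8 from then on
- loss either abrupt, or preceded by a recorded linear decline over the three previous visits
- model with group-by-visit means and unstructured covariance, fitted by maximum likelihood; 150 runs per scenario

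Attenuation = 1 − estimated/true, where true counts the value 8 after loss.

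| Loss pattern | Viremic / non-viremic loss | True deficit | Completers only | Mixed model | Attenuation |
|---|---|---|---|---|---|
| Decline recorded | 5% / 1% | 4.71 | 2.93 | 4.04 | 14% |
| Decline recorded | 10% / 1% | 7.14 | 3.01 | 5.64 | 21% |
| Decline recorded | 15% / 1% | 8.78 | 2.90 | 6.74 | 23% |
| Abrupt | 5% / 1% | 4.70 | 2.94 | 2.96 | 37% |
| Abrupt | 10% / 1% | 7.14 | 3.23 | 3.19 | 55% |
| Abrupt | 15% / 1% | 8.92 | 3.07 | 3.08 | 65% |
| Decline recorded | 2% / 2% | 3.53 | 3.39 | 3.50 | none material |
| Abrupt | 2% / 2% | 3.05 | 3.16 | 3.17 | none material |

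**3. Reading the table.** Where the decline was recorded, the model recovered 62 to 65% of the gap between completers and the full effect; at 5% loss, (4.04 − 2.93)/(4.71 − 2.93) = 62%. Where loss was abrupt it recovered essentially nothing. The bias comes from the difference in loss rates between the groups, not from graft loss as such.

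**4. Outer limit on the plan's scale.** Suppose the true difference counting losses is 5.9, loss is 5% against 1%, baseline is 55, the value after loss is 8, and nothing is recovered. The fall at loss is 55 − 8 = 47, and the difference left is (5.9 − 0.05 × 47 + 0.01 × 47)/0.95 = 4.02/0.95 = 4.23. Power with 38 and 406 subjects is then about 63%.

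**The case against.** The strongest reply is that most of the decline will be seen. GFR up to termination stays in the model. Subjects still viremic are sampled about every two weeks (section 4.3), and section 2.1.1 describes the decline as running over months. Dropout that follows recorded low values is close to ignorable. Losses by Month 12 may also be few: section 5.3.2 excludes proven or suspected BKVN at entry, plasma PCR is run in real time (section 7.5), physicians may modify immunosuppression (section 7.4), and section 2.1.1 reports a marked fall in graft loss at some institutions after such modification. A graft lost before viremia is detected would count in the non-viremic group, which works against the expected direction.

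Much of this stands. It makes the smaller attenuation the more plausible one and the direction conditional. It does not supply a rule for graft loss, and bias remained in the simulation even when the decline was recorded.

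A reader might infer three stronger things that the documents do not support:

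- **That subjects with graft loss disappear from the comparison.** Only their values after termination are absent.
- **That the background figures bound the number of losses.** BKVN in 1 to 10% of 450 subjects with 30 to 70% deteriorating gives 450 × 0.01 × 0.30 = 1.35 to 450 × 0.10 × 0.70 = 31.5. But section 2.1.1 speaks of eventual loss in some studies, with no 12-month time frame. The upper end also needs 450 × 0.10 = 45 BKVN cases, virtually all viremic, against about 40 viremic subjects expected.
- **That 2 to 4 of the targeted 5.9 units are hidden.** This takes four losses among 40 and an unseen further fall of 20 to 40 (4/40 × 20 = 2; 4/40 × 40 = 4). Neither figure has a source. A further fall of that size to about 10 would need a last recorded GFR of roughly 30 to 50.

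**Conclusion.** The gap is real. The plan ends observation at an event caused by the outcome, analyses only what was observed, and does not say how graft loss or death enters a comparison that serves a primary objective. If graft loss is more frequent among viremic subjects, the estimated GFR deficit is biased toward no difference. If the rates are equal, there is no material bias.

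The size cannot be fixed from the documents. About 14 to 23% attenuation (decline recorded) and 37 to 65% (abrupt loss) hold only under the assumed losses of 5 to 15% against 1%, the assumed baseline GFR and variances, and a value of 8 after loss. The planned two-weekly sampling favours the lower range. The planned model remains usable. It should not stand alone as evidence that viremia has little effect on GFR.

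**What to change.** In section 8.4.1, keep the planned mixed model and add one pre-specified sensitivity analysis:

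- For subjects with graft loss (GFR below 10, chronic dialysis or re-transplantation), set GFR to 10, the protocol's own graft-loss bound, from the event through Month 12 post-transplant.
- Assign the value on the same monthly, then two-monthly, post-transplant grid in both groups (the visit months of Appendix A-1). Do not assign it at the two-weekly intensive visits, which have no fixed number and would put many extra values into one group only.
- Report graft losses and deaths by viremia group beside the result.
- State how deaths with a functioning graft are handled.

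The cost is one further analysis, with no change to visits, sample size or termination rules. The events and the reasons for termination are already documented. Sections 4.6, 6.2 and 6.3 do not mention event dates, so confirm that the eCRF captures them.

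The downside is that 10 is a convention and widens the variance. As an illustration, if 10% of viremic subjects are lost and the assigned value lies 20 to 40 below what they would otherwise have had, the added variance in that group is 0.10 × 0.90 × 20² = 36 to 0.10 × 0.90 × 40² = 144, against 10.9² = 119. The analysis therefore supplements the planned one and does not replace it.
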